Primary Aim: To determine if a 48 hour maximum dwell time reduces bacterial contamination and biofilm formation of feeding tubes, feeding tube hubs, and intraluminal fluid in premature VLBW infants. **Primary hypothesis**: Feeding tubes which remain in place 0-48 hours will have less contamination and less biofilm formation compared to those left in place for 7 days.

Aim 2: Compare gastrointestinal microbial dysbiosis and inflammation between Group 1 and Group 2. **Hypothesis:** Infants in Group 1 will have less GI microbial dysbiosis and inflammation compared to Group 2.

Aim 3: Determine the effect of feeding tube dwell time and feeding tube contamination, and biofilm formation on selected health outcomes in premature VLBW infants. **Hypothesis:** Infants in Group 1 will have lower odds for necrotizing enterocolitis and late onset sepsis, and improved nutritional outcomes compared to Group 2.

5. Research Plan:

A randomized controlled trial will be conducted to determine whether feeding tube dwell time is associated with level of feeding tube contamination. Infants will be randomly assigned to have their feeding tubes removed at 0-48 hours or 7 days for the first 4 weeks of life. The feeding tube lumen, interluminal liquid and hub will be analyzed for level of contamination.

Sample and Setting

The proposed study will follow a prospective cohort (N =151) premature VLBW male and female infants for 4 weeks following birth. If the mother is providing breast milk to her infant, she will also be included in the study since she will be providing 2 samples of her breast milk for analysis.

Inclusion criteria are: 1) be born to a mother who is at least 18 years of age and English or Spanish speaking, 2) born at \leq 30 weeks 3) have a birthweight \leq 1500 grams, 4) be born to a mother who is COVID Negative, 5) have a feeding tube placed within 24 hours of birth and 5) be expected to require a feeding tube for 4 weeks following birth.

Exclusion criteria are: 1) Infant with known congenital GI anomalies, (2) are not expected to live, or (3) Infants will be withdrawn from the study if they require abdominal surgery for GI morbidities.

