Data integrity will be evaluated using descriptive statistics (e.g.: means, standard deviations, frequencies, percents, range) appropriate for measurement level. Checks for implausible or outof-range values, distributional forms, the presence and distribution of censored values (e.g.: inflammatory markers), and missingness will be performed. Data transformations (e.g.: Box-Cox family of transforms) will be made, if required, based on evaluation of model fit and tenability of assumptions. If applicable, regression techniques which can accommodate censored variables (e.g. MPLUS version 8 or higher)⁵⁸ will be employed. Selected variables (e.g.: type of feed (mother's breast milk or donor breast milk), whether NPO, antibiotic use, gestational age, chronological age, gastric pH and sex) will be screened for potential inclusion as covariates in each of the statistical models tested. Associations between each potential covariate and the respective dependent variable will be examined, and only those variables having a p<.10 association and whose inclusion improves model fit will be retained. The general modeling strategy will be a generalized linear mixed model (GLMM) approach. A GLMM is able to accommodate different numbers of measurements between subjects, utilize data from subjects when some of the data is missing (that is, subjects with some missing data points will not be dropped from analysis), can incorporate time-varying covariates, flexible covariance structures, and a variety of dependent variable distributions (including dichotomous), and thus will be able to accommodate the analyses proposed. Model fit and strength of association will be evaluated using Vonesh's GOF macro for SAS. Our primary goal will be to assess differences in marginal least squares means between the dwell time groups. All analyses will be performed using SAS software version 9.4 or later. Statistically significant interaction effects will be evaluated using simple main effects analyses via the SLICE option available in the SAS/STAT GLMM procedures. Due to the number of inferential tests planned, it is not practical to maintain a 5% experiment-wise Type I error rate; however, significance levels will be adjusted to maintain a model-wise 5% Type I error rate through use of a Benjamini-Hochberg approach.

Data Entry and Management

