A code key stored separate from the data set will be used. The code key will be kept in a locked cabinet in the research office. All data will be entered into a REDCAP database having integrated data quality and consistency checks. The study database created in REDCap will be password-protected and housed on a designated database server. Data quality will be monitored and assured as reported and as entered into the database. All hardcopy forms will be

Variable	Measurement	Timing
Descriptive (1-2) below		
1. Maternal, prenatal and perinatal demographics	Maternal history, prenatal and perinatal complications and medications, mode of delivery, antibiotic use, steroid use	Collected upon entry into study.
2. Infant demographics	Race/ethnicity, sex, gestational age, birth weight, Apgar scores, resuscitation at birth and neonatal acuity (SNAP II) score, type of feeding, whether or not the infant is NPO, medications effecting gastric pH, chronologic age, NPO, number of days and type of antibiotics	Collected upon entry into study and during the 4 week study period. Antibiotic data tracked for 6 weeks
Microbial analysis of feeding tubes, feeding tube hubs and residual intraluminal liquid Analysis of gastric contents (1-2)	Culture based analysis and microbial analysis (16S rRNA and metagenomics sequencing). Presence of biofilm in feeding tube or Replogle tube	Following removal of each feeding tube for 4 weeks
below		
1. Microbial analysis	16S rRNA and metagenomics sequencing	Weekly for 4 weeks
2. Inflammatory markers	Analysis of inflammatory markers	Weekly for 4 weeks
3. pH testing	Measuring acidity	Initially and weekly for 4 weeks
Analysis of stool (1-2) below		
1. Microbial analysis	16S rRNA and metagenomics sequencing	Weekly for 4 weeks
2. Inflammatory markers	Analysis of inflammatory markers	Weekly for 4 weeks
3. pH testing	Measuring acidity	Weekly for 4 weeks
Nutritional outcomes (1-6) below		
1. Enteral intake	24-hour enteral feeding intake in mL/kg	Daily for 6 weeks
2. Time to full feeds	First day infant received ≥120 mL/kg/d of enteral feedings. First day infant received 150ml/kg/d	Recorded daily until 150 mL/kg/d reached (up to 6 weeks)
3. Hours of PN	Number of hours infant received some parenteral nutrition	Daily for up to 20 weeks

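### The contamination and biofilm part of Aim 3 is not randomised, yet its confounders are chosen only by a p<.10 association with the outcome plus improved fit; the possible bias ranges from negligible to material

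*Combined protocol and SAP*

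**What the plan says.** Aim 3 is worded to cover three exposures: "Determine the effect of feeding tube dwell time and feeding tube contamination, and biofilm formation on selected health outcomes in premature VLBW infants". Only the first is assigned at random. Contamination and biofilm are measured on tubes after removal. The hypothesis attached to the aim concerns the randomised groups alone: "Infants in Group 1 will have lower odds for necrotizing enterocolitis and late onset sepsis, and improved nutritional outcomes compared to Group 2".

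The Statistical Analysis section gives one covariate procedure. Selected variables "will be screened for potential inclusion as covariates in each of the statistical models tested". The test is on the outcome side only: "Associations between each potential covariate and the respective dependent variable will be examined". The section then sets two conditions for keeping a covariate, a p-value and better fit: "only those variables having a p<.10 association and whose inclusion improves model fit will be retained". The candidates are given as examples: type of feed, then "whether NPO, antibiotic use, gestational age, chronological age, gastric pH and sex". None is forced into any model. The same section states the main target as follows: "Our primary goal will be to assess differences in marginal least squares means between the dwell time groups".

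The data table under Data Entry and Management shows that further severity measures are collected: "Race/ethnicity, sex, gestational age, birth weight, Apgar scores, resuscitation at birth and neonatal acuity (SNAP II) score". Birth weight and SNAP II are not among the named candidates. No separate model is written for contamination or biofilm as an exposure, so the general procedure applies by default.

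**The concern.** A variable confounds the contamination estimate if it is related both to contamination and to the outcome. The screen examines only the second relation, and does so with a p-value. When events are few, a p-value threshold has little power to keep a variable that matters.

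For the randomised dwell-time contrast, dropping a baseline covariate mainly costs precision. For contamination or biofilm it can leave bias. If less mature or sicker infants also have more contaminated tubes, contamination could appear to raise the risk of NEC or sepsis when it does not. The Background section presents contamination as a route to these morbidities, so such a result would be read as support for the trial's rationale. The Benjamini-Hochberg adjustment deals with multiplicity and does not remove confounding.

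**Working it through.** **The plan's own figures.** None is given for Aim 3. The 134 enrolled fits 120 analysable infants (120/0.90 = 133.3, rounded up), although 120 is not stated. The primary-aim power of .97 cannot be recomputed without the pilot means and covariance matrix, and it does not bear on this point.

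**Inputs from the documents.** Analysable infants: 134 × 0.90 = 120.6, so 120 or 121. The sample section gives 151 instead, and 151 × 0.90 = 135.9, so 136. The rule is p<.10 plus improved fit.

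**Assumptions not in the documents.** Event rate 7-30%, with 8% as the NEC-like case (0.08 × 121 = 9.7 events). Confounder odds ratio 1.5-2.0 per SD. Correlation of each confounder with contamination 0.3-0.5 (0.3-0.4 where three act together). One outcome record per infant. Improved fit read as a lower AIC. Contamination tested at 5% two-sided. True contamination effect zero.

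**Step 1: how often the screen drops one confounder.** For a covariate scaled to SD 1, the standard error of its log odds ratio is roughly 1/√(n·p·(1−p)). The chance of missing p<.10 is roughly Φ(1.645 − log OR/SE).

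- 8% events, n=121: SE = 1/√(121 × 0.08 × 0.92) = 0.335. OR 1.5: Φ(1.645 − 0.405/0.335) = Φ(0.435) = 67%. OR 2.0: Φ(1.645 − 0.693/0.335) = Φ(−0.42) = 34%.
- 30% events, n=121: SE = 1/√(121 × 0.30 × 0.70) = 0.198. OR 1.5: about 34%. OR 2.0: about 3%.

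Simulation with the fit condition added agrees:

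- At 8% events the confounder is dropped in 39-73% of trials over OR 1.5-2.0.
- At n=120 and event rates of 7-30%, OR 1.5 is dropped in 39-76%.
- OR 2.0 is dropped in 32-50% at 7-10% events and in 5-17% at 20-30%.
- At n=136, OR 1.5 and 10-20% events, it is dropped in 44-67%, so the larger sample does not change the picture.

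**Step 2: what the dropping does with one confounder.** The false-positive rate for contamination is 5.3-6.7% at correlation 0.3 and 7.2-9.5% at 0.5, against 4.7-6.5% with the confounder forced.

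**Step 3: three confounders, 8% events, n=121.**

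| Relation among the three confounders | False positives under the rule |
|---|---|
| Independent, same direction | about 9-24% |
| Correlated 0.2-0.3, same direction | about 5-10% |
| Correlated 0.5, same direction | about 4-6% |
| Independent, one direction reversed | about 5-8% |
| All three forced, for comparison | about 4-6% |

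In the independent, same-direction setting, forcing all three raised the standard error of the contamination estimate by about 12-35%.

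**Step 4: other outcomes.** For a continuous outcome at n=120, a single confounder correlated .15-.20 with the outcome is dropped in 33-57% of trials, one at .30 in 4-8%, and one at .40 in under 1%. Four independent same-direction confounders give 9-21% false positives against about 5% forced. The same four-confounder set-up with a binary outcome at 7-30% events gives 13-24% against 5.6-7.9%. Both of these results also rest on independence.

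**The case against.** The strongest objection is about size. A reader might infer from the independent, same-direction result that the rule makes a spurious contamination effect likely. The documents do not support that. They give no event rate, no effect sizes and no correlations. Immaturity, acuity and antibiotic exposure would be expected to move together, and then the covariates that pass the screen stand in for those that do not. Antibiotics could also act in the opposite direction. In either case most of the excess disappears. This objection stands and sets the size of the point.

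The next objection is scope. The Aim 3 hypothesis and the stated analysis goal are both the randomised contrast, and no contamination model is written out. This stands as a reason for low severity. It does not remove the concern, because the aim names both exposures and the covariate rule covers every model.

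It can also be said that SNAP II is missing from the candidates because of the list, not because of the threshold. That is correct, but the list is only illustrative and anything added to it must still pass the screen.

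Finally, forcing variables in has costs of its own. The data table defines presumed late-onset sepsis by antibiotic treatment of at least 3 days with negative cultures, so a raw count of antibiotic days can contain the outcome. Forcing randomised group removes the randomised variation in contamination. Both objections stand and shape the fix.

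**Conclusion.** The point holds as a minor one. The rule as written can leave confounding in the contamination and biofilm part of Aim 3, because it ignores the relation to the exposure and often drops moderate confounders when events are few. Strong confounders of common or continuous outcomes are usually kept.

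The effect on error rates cannot be fixed from the documents. On the assumptions above it lies anywhere from no visible excess to a rate several times the nominal 5%, and the high end needs several mutually independent confounders pushing the same way. These figures are for one test at 5% in a simplified model with one record per infant, not for the planned repeated-measures model.

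A reader might also infer that the dwell-time comparison is biased by this route. It is not, since allocation is random and omitting a baseline covariate does not confound it.

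**What to change.** In the Statistical Analysis section, exempt the Aim 3 contamination and biofilm models from the p<.10 and fit screen, and state instead that:

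- gestational age and SNAP II, both already collected, are always included whatever their p-values;
- antibiotic exposure is also included, counted only up to the earlier of the tube sample and the onset of the outcome episode;
- penalised likelihood is used where events are few;
- results are shown with and without randomised group, as a sensitivity analysis;
- results are reported as adjusted associations, not effects.

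The change is to wording and needs no new variables. The antibiotic item does need dated records: the data table lists number of days and type, and the team should confirm that dates can be recovered. The price is wider intervals, with standard errors up to about a third larger for a rare outcome such as NEC.

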Following consent, data including gestational age, chronologic age, birth weight, race, gender, date and time of sample collection, feeding tube dwell time, duration of antibiotic therapy since birth, episodes of sepsis, other medications, mode of delivery, and mode and type of feeding will be obtained from the EMR. Other data including incidence of stage 2 or greater necrotizing enterocolitis; episodes of presumed or culture proven late onset sepsis (occurring > 3 days of life); days to discharge; nutritional outcomes, including weekly enteral intake, days to full enteral feedings (120 mL/kg/d),(150ml/kg/day), hours of parenteral nutrition, evidence of PNALD (level of direct bilirubin, alkaline phosphatase, aspartate aminotransferase (AST) and alanine aminotransferase (ALT); growth indices (weekly weight, head circumference and length); and hours with a central venous line will be collected.

Infants in both groups will have a bedside sign and EPIC note stating which group they are assigned to and when they are scheduled for feeding tube replacement. Infants will have their feeding tubes replaced 0-48h (Group 1) and every 7 days (Group 2). At the designated time, the feeding tube will be replaced by either the bedside nurse or the research coordinator (an experienced NICU nurse) using the NICU's standard method of feeding tube insertion.

All tubes will be adhered to the infant's face using the same procedure designed to decrease the risk of feeding tube dislodgement and protect skin integrity. The method of tube securement will be approved by NICU management/staff and comply with NICU skin care guidelines. The orogastric tubes will be taped to the chin from the middle of the mouth and nasogastric tubes will be taped under the lateral edge of nares. The research team will check the security of the tube adherence 3x per week and re-secure as necessary. On the day that the study feeding tube is scheduled to be removed, the research coordinator will coordinate with the bedside nurse when the feeding tube will be removed and replaced. In the event the infant has a Replogle tube instead of a feeding tube on lab collection day, the Replogle tube will collected. At the designated time, the feeding tube or Replogle will be removed and immediately placed in a sterile Ziploc bag and placed on ice for immediate transfer to laboratory by member to research team.

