1.PNALD	Liver function tests (level of direct bilirubin, alkaline phosphatase, AST and ALT)	Weekly or biweekly for 6 weeks Peak alkaline phosphatase and Peak direct bilirubin for up to 20 weeks or discharge
2. Hours of central venous line access	Number of hours infant has a central venous line	Daily for up to 20 weeks
3. Growth indices	Weight, length, and head circumference	Daily for 4 weeks and at discharge
4. Episodes of late onset sepsis	Episodes of culture proven or presumed sepsis (treated with \geq 3 days of antibiotics but with negative cultures)	Daily from birth up to 20 weeks
5.Episodes of NEC	Episodes of radiologic or surgical evidence of NEC	All incidences for up to 20 weeks
6. Length of hospital stay	Days infant remains in hospital	From birth until discharge
Covariates (1-5) below		
1. Gastric pH	pH of gastric aspirates, use of medications which affect gastric pH	Gastric pH analysis will be done weekly, information regarding medications will be collected during the 4 weeks study period
2. Oropharyngeal swabs	Time of last feed, oral medications	Sputum samples weekly for 4 weeks
3.Analysis of maternal breast milk or donor milk	Microbiota and metagenomic sequencing	At week 1 and week 4

4. Nutritional data	Medications and disease processes associated with decreased intestinal motility, episodes and duration of kangaroo care	Upon entry into study and for 4 active weeks.

visually inspected before data entry. A manual comparison of randomly selected data hardcopy forms with data output listing generated from the study database will be performed, and consistency checks will be generated by SQL or SAS programs as part of data cleaning procedures. The system will assign a global unique identifier to each enrolled subject that will serve as the subject id. Study case report forms (CRFs) will be maintained in study specific folders and when CRFs not actively being processed, will be secured in locked file cabinets. In addition to the use of passwords and other security measures, all documents containing identifying information are considered confidential materials and will be safeguarded. Data to be collected are found in Table 3. Data collected in REDCap will be shared with an outside affiliated researcher at Old Dominion University for secondary data analysis. All data sets shared will be verified with CTSI REDCap, before giving outside researcher access.

7. Possible Discomforts and Risks:

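### Aim 3 sets an odds comparison for NEC, but the only planned method has no finite odds ratio when an arm has no events, and no sparse-event method is specified

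*Combined protocol and SAP*

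**What the plan says.** The Aim 3 hypothesis is "Infants in Group 1 will have lower odds for necrotizing enterocolitis and late onset sepsis, and improved nutritional outcomes compared to Group 2", so NEC is to be compared on the odds scale.

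The Statistical Analysis section states: "The general modeling strategy will be a generalized linear mixed model (GLMM) approach". It adds that such a model can take "a variety of dependent variable distributions (including dichotomous), and thus will be able to accommodate the analyses proposed". Candidate covariates are screened for every model, and "only those variables having a p<.10 association and whose inclusion improves model fit will be retained". No Aim 3 model is written out, and no other method for binary outcomes is named.

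NEC is described in two ways. The Procedure section collects "incidence of stage 2 or greater necrotizing enterocolitis". The variable table under Data Entry and Management lists "Episodes of radiologic or surgical evidence of NEC", with timing "All incidences for up to 20 weeks". Neither says how the records become one result per infant.

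The power section covers the culture outcome only. I found no NEC risk, expected event count, sparse-event method, rule for non-convergence or limit on the number of covariates.

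**The concern.** The advantages claimed for the mixed model (unequal numbers of measurements, time-varying covariates, flexible covariance) suit the weekly tube data. They do nothing for an outcome with one value per infant. There, a random infant effect has no within-infant replication to estimate it, and what remains is ordinary logistic regression by maximum likelihood.

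That method fails in a known way. If no infant in one arm has NEC, the estimated group odds ratio is zero or infinite, its Wald interval is meaningless, and the software reports separation or non-convergence. With no planned alternative, the team would choose one after seeing the data, for a named clinical hypothesis.

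**Working it through.** **The plan's own figure.** The only stated power is a lower 99% limit of .97 for the dwell group by colony type interaction. It comes from a simulation whose pilot means and covariances are not printed, so it cannot be re-run. It says nothing about NEC.

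**Inputs.**
- Infants: the power section enrols 134 with 10% loss, and 134 × 0.9 = 120.6, or about 120 evaluable. Sample and Setting gives 151. I use n = 60, 67 and 75 per arm (N = 120, 134, 150).
- Allocation: ratio not stated; 1:1 assumed.
- Group 2 NEC risk p2: not given; 3%, 5%, 8% and 12% assumed.
- True odds ratio: 0.5 assumed.

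**Step 1: chance of an empty arm.** Let o = p2/(1 − p2) and p1 = 0.5o/(1 + 0.5o). With a = (1 − p1)^n and b = (1 − p2)^n, the chance that at least one arm has no events is a + b − ab.

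Example, p2 = 5% and n = 60: o = 0.0526 and p1 = 0.0256. Then a = 0.210, b = 0.046, ab = 0.010, and the chance is 0.247.

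| Group 2 risk | Group 1 risk | N = 120 | N = 134 | N = 150 | Expected events, N = 134 |
|---|---|---|---|---|---|
| 3% | 1.5% | 50% | 44% | 39% | 3.0 |
| 5% | 2.6% | 25% | 20% | 16% | 5.1 |
| 8% | 4.2% | 8% | 6% | 4% | 8.2 |
| 12% | 6.4% | 2% | 1% | 1% | 12.3 |

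Expected events are 67 × (p1 + p2).

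**Step 2: do the screened covariates add to this?** A simulation applied the p<.10 screen to seven candidates, one of them prognostic (250 runs per setting, N = 134, Group 1 risk set to half of Group 2 risk). The screen kept about 0.5 to 1.1 covariates on average. The group odds ratio diverged in 19% of runs at 5% vs 2.5% and in 10% at 7% vs 3.5%, the same as without covariates. Some coefficient, not necessarily the group one, was infinite in 24% and 16%. Forcing in all seven raised that to 55% and 34%. Under the planned procedure, then, a non-finite group odds ratio comes almost wholly from empty arms.

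**Step 3: what the alternative returns.** For a 2×2 table the Firth estimate equals adding 0.5 to each cell. With 67 per arm:
- 0 vs 4 events: (0.5 × 63.5)/(4.5 × 67.5) = 0.10, Wald 95% interval 0.01 to 2.02.
- 2 vs 5: (2.5 × 62.5)/(5.5 × 65.5) = 0.43, interval 0.09 to 2.04.
- 3 vs 7: (3.5 × 60.5)/(7.5 × 64.5) = 0.44, interval 0.12 to 1.65.

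The risk difference is also reportable. For 0 vs 4 it is 0 − 4/67 = −6.0 points. The Wilson score limits are 0 to 0.0542 for 0/67 and 0.0235 to 0.1437 for 4/67. The combined limits are −0.0597 − √(0² + 0.0840²) = −0.144 and −0.0597 + √(0.0542² + 0.0362²) = 0.006.

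**Step 4: is low power the model's fault?** At 60 per arm and odds ratio 0.5, Fisher's exact test (two-sided .05) rejects in 0.4%, 2.0%, 5.6% and 10.3% of trials at the four risks. In a five-covariate logistic fit the Wald test, where it converged, rejected in 0.2%, 2.6%, 6% and 12%. The two are much alike, so the low power comes from the small number of events.

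**The case against.** The best defence is that the mixed model is only a general strategy. No Aim 3 model is written out, so nothing obliges the team to fit an infant random effect to NEC, and dropping it stays within the same model family. That is fair, and the random effect alone would do little harm. It does not answer the empty-arm problem, which ordinary logistic regression shares.

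Three stronger readings are tempting and are not supported.

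- **That the method will often fail because NEC is rare.** The documents give no NEC risk. At 8% to 12% a non-finite group odds ratio occurs in about 1% to 8% of trials. With no true effect the chance is also lower: at 5% risk in both arms it is 9%, 6% and 4% for N of 120, 134 and 150. Forcing five covariates into every fit at 60 per arm gives 65%, 40%, 13% and 3% at the four risks, but the plan screens covariates and does not force them in.
- **That the planned test is to blame for low power.** Step 4 shows that an exact test does no better.
- **That NEC would yield no usable result.** Counts and percentages by group remain available with an empty arm. The plan mentions such summaries only for data-integrity checks, so they are not yet a planned NEC analysis.

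One yes/no per infant is itself an inference from the word odds, since the variable table records episodes. That is a further reason to define the endpoint.

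**Conclusion.** The point stands in a limited form. For NEC the plan offers only a model that reduces to maximum-likelihood logistic regression, with no per-infant endpoint and no sparse-event method. The chance of a non-finite group odds ratio is about 1% to 50%, given an odds ratio of 0.5, 1:1 allocation, Group 2 risks of 12% down to 3% and N of 120 to 150. All but N are assumptions, and N itself is 134 in one section and 151 in another.

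This concerns one component of the third aim and leaves the primary analysis untouched. It merits a change because the remedy is cheap and avoids a choice of method after the data are seen.

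A related conflict bears on the event count. The exclusion criteria withdraw infants who need abdominal surgery for GI morbidity, while the variable table counts surgical NEC for up to 20 weeks. If withdrawn infants' outcomes were dropped, events would be fewer than shown here.

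**What to change.** Add to the Statistical Analysis section:

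1. NEC is analysed as any episode per infant, one row per infant, with no random effect. Reconcile the two descriptions of NEC so that a single definition applies.
2. The odds ratio comes from Firth-penalised logistic regression (FIRTH option in SAS PROC LOGISTIC), with no p<.10-screened covariates and at most gestational age, fixed in advance.
3. Event counts by group and the risk difference, with a score or exact confidence interval, are reported alongside the odds ratio. These still serve if neither arm has an event.
4. The NEC comparison is described as imprecise, because the method does not raise power.
5. The surgery-withdrawal criterion and the surgical NEC entry are reconciled so that withdrawn infants' NEC outcomes are not lost. The 134 and 151 are reconciled too.

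The cost is a few sentences and a standard option in software the plan already names. The downside is slight shrinkage of the odds ratio and less covariate adjustment. No new infants or samples are needed.

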Sample Size Determination/Power Analysis: The primary aim of this study is to test for associations between feeding tube dwell time and the bacterial load present in the feeding tube. Pilot study results were used to estimate variance for the log transformed values of bacterial load observed in cultures. The study employs a repeated measures design, with measurements performed on each neonate each week of the 4 week study duration. For the primary bacterial contamination aim, each measurement consists of measures from 5 individual feeding tube sections for 5 individual colony types, providing a total of 100 within-subjects data points per neonate. Given the repeated measures design and the incorporation of selected covariates, a Generalized Linear Mixed Model (GLMM) analysis is planned for the primary aim. The data derived from the pilot study of 31 feeding tubes informed the covariance structure and means vectors for entry into PASS 14's procedure which estimates mixed models power using simulation. Using a .005 level of significance (in recognition of the multiple inferential tests), 400 simulation samples, a minimum detectable difference of 3.0 (natural log transformed colony forming units), and employing the pilot data to inform mean vectors and the unstructured covariance matrix for the simulations, the lower 99% confidence limit for power is .97 for the Dwell Group by Colony Type interaction, which is of primary interest. To accommodate the anticipated 10% loss due to surgery or death, 134 neonates will be enrolled. If mothers are providing breast milk samples, 151 mothers would also be enrolled.

Standard Infant Feeding Protocol

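### Benjamini-Hochberg does not deliver the model-wise 5% Type I error rate that the plan attributes to it; what it controls is the false discovery rate

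*Combined protocol and SAP*

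**What the plan says.** The Statistical Analysis section first gives up study-wide control: "it is not practical to maintain a 5% experiment-wise Type I error rate". It then makes a narrower promise, that "significance levels will be adjusted to maintain a model-wise 5% Type I error rate through use of a Benjamini-Hochberg approach". The false discovery rate is mentioned nowhere in the document.

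The same section gives two kinds of inference within a model. One is overall: "Our primary goal will be to assess differences in marginal least squares means between the dwell time groups". The other is conditional: "Statistically significant interaction effects will be evaluated using simple main effects analyses via the SLICE option". No section lists the tests that enter the adjustment for the primary model.

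The Sample Size Determination/Power Analysis section describes the primary data as "measures from 5 individual feeding tube sections for 5 individual colony types", repeated over four weeks. Its power statement is set at a fixed level, "Using a .005 level of significance (in recognition of the multiple inferential tests", and reports that "the lower 99% confidence limit for power is .97 for the Dwell Group by Colony Type interaction, which is of primary interest".

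**The concern.** Set against the experiment-wise rate that the plan disclaims, a model-wise Type I error rate reads naturally as the chance of at least one false positive among the tests in one model. Benjamini-Hochberg targets something else, the expected share of rejections that are false. The two agree when every null is true. They part when some effects are real, because each real effect that is rejected loosens the threshold for the remaining tests.

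That mixed case is the one the trial is designed around. A dwell-by-colony-type interaction means that dwell time matters for some colony types more than for others. If a report then flags particular colony types and cites 5% Type I error control, it claims a guarantee that the method does not give.

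**Working it through.** **1. Where the plan's 5% is reproduced, and where it is not.** Take five tests, one per colony type (five types are in the sample-size section; five tests is an assumption). Benjamini-Hochberg finds the largest k for which the k-th smallest p-value is at most k × .05/5 = .01k, and rejects the k smallest. Suppose the tests are independent and the real effects are large enough always to be rejected. With m0 true nulls, the smallest null p-value is then compared with .01 × (5 − m0 + 1).

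- m0 = 5: 5%. The plan's figure is reproduced.
- m0 = 1: threshold .05, so 5%. Reproduced again.
- m0 = 2: thresholds .04 and .05. Chance of any false positive = 1 − .96² + (.05 − .04)² = .0784 + .0001 = 7.85%.
- m0 = 3: threshold .03 for the smallest. 1 − .97³ = 8.7%, before small added terms.
- m0 = 4: threshold .02 for the smallest. 1 − .98⁴ = 7.8%, before small added terms.

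Under Holm the smallest null p-value is compared with .05/m0, so the chance stays at or below 5%.

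**2. Adding the interaction gate.** The follow-up comparisons run only after a significant interaction. With 2 groups and 5 colony types the interaction has (2 − 1)(5 − 1) = 4 degrees of freedom. The .97 cannot be rebuilt, because the pilot means and covariance are not given. It fits about 396 of 400 significant simulations (exact lower 99% limit .969). It can be used for calibration: a 4-df chi-square test at .005 has power .97 at noncentrality 29.2. With equal real effects of size z and correlation ρ between tests, noncentrality = z² × m0(5 − m0) / [5(1 − ρ)], so

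z = √[29.2 × 5(1 − ρ) / (m0(5 − m0))].

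At ρ = 0 this gives √(146/6) = 4.9 for m0 = 2 or 3, and √(146/4) = 6.0 for m0 = 4. At ρ = .5 it gives 3.5-4.3, and at ρ = .75 it gives 2.5-3.0.

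**3. Results by simulation** (two-sided z tests, 2-4 true nulls, gate at .05 or .005). The second column is Benjamini-Hochberg on the five gated comparisons. The third applies it to seven tests (the interaction, the marginal dwell-group difference and the five comparisons) and counts a comparison only if the interaction is also rejected.

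| Correlation | Any false positive, five gated tests | Any false colony-type finding, seven tests |
|---|---|---|
| 0 | 7.2-8.7% | about 8-10% |
| .5 | 5.9-6.8% | 6.4-7.9% |
| .75 | 4.0-4.5% | 4.8-5.6% |

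Holm on the five stays at or below 5.0% throughout. The false discovery rate under Benjamini-Hochberg on the five is 1.2-4.0%. For modest effects (z = 3) the gate brings the chance of any false positive down to 4.0-6.5%. With all five null it is 0.2-2.4% with the gate.

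The gate therefore protects well when nothing is real, but does little at the effect size the trial is powered for, because the interaction then passes about 97% of the time or more.

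**The case against.** The strongest reply has four parts.

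- **The method is named in the same sentence.** The plan also openly gives up experiment-wise control, so a statistician can work out the true property. This limits the harm. It does not make the stated property correct, and readers of a results paper may see only the 5% claim.
- **The excess depends on assumptions.** This stands. The plan says only simple main effects. Slicing within dwell group would give two tests, and with two tests and one true null Benjamini-Hochberg does not exceed 5%. Comparing dwell groups within colony type is the more natural reading, but the document does not say so. High correlation between tests on the same neonates shrinks the excess and, for five tests, removes it.
- **The gate already protects.** This is true for null or modest effects, much less so at planned effects.
- **Benjamini-Hochberg does control something useful.** This also stands, under independence or positive dependence, a condition that any restated promise should carry.

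Three stronger readings are tempting and go too far. A reader might infer error rates of 14-29%. Those arise only with 10 to 25 independent tests, about half of them null, and no gate, and the document states no such family. A reader might infer that the .005 level shows the power to be overstated. It equals .05/10, but no count of ten tests is given, and the power figure was computed for one interaction at that level. The mismatch is one of alignment. A reader might also see a contradiction between the interaction as the main interest and marginal means as the main goal. The two can be read together, and what is missing is a statement of which is the primary test.

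**Conclusion.** The sentence is wrong as written: Benjamini-Hochberg does not in general maintain a 5% chance of any false positive within a model. That conclusion needs none of the simulation assumptions, and confidence in it is high.

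The size is illustrative. At the plan's own interaction power the excess over 5% is up to about 4 percentage points for five gated comparisons and about 5 for the seven-test family, and it is small or absent at correlation .75. These figures rest on the assumed family, two to four true nulls, real effects of equal size and the assumed correlation. The .97 is a lower confidence limit, so the planned effects may be larger than those used here.

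The documents do not support a claim that the analysis lacks error control or that the trial is underpowered. Severity is minor to should-fix. The unlisted tests, the choice of primary test and the link to .005 are secondary clarifications.

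**What to change.** **Preferred: restate the property.** For example: *within each model the false discovery rate is held at 5% by Benjamini-Hochberg, assuming independent or positively dependent tests.* Reports should then not describe flagged colony types as having 5% Type I error control. This is a change of wording and costs no power.

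**Alternative: keep the 5% Type I error promise and use Holm on the five colony-type comparisons after a significant interaction.** The cost in power per real comparison at planned effects is about 0-0.3 percentage points (independent), 0.3-4.4 (correlation .5) or 0.1-6.8 (correlation .75), and up to about 7 for modest effects. Holm over all seven tests costs more, about 1, 2-7 and 7-11 points respectively at planned effects, so it should be limited to the five comparisons.

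In the same edit, list the tests in the chosen family. It would also help to say whether the interaction or the marginal dwell-group difference is the primary test, and how the .005 in the power calculation relates to the rule adopted. No new data are needed.
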